Recruitment. Individuals with physician-confirmed RA will be targeted in this study. Patients will be recruited via physician referral from the Johns Hopkins Arthritis Center, which is directed by Co-I [name], or via IRB-approved advertisements.

Screening and Randomization:

Telephone Screen: Participants will undergo an initial screen over the phone (or in person if they are initially identified in the Arthritis Center Clinic), prior to informed consent. Participants meeting initial screening criteria will be scheduled for a subsequent screening session.

Screening Session (Session 1): At the screening session (either remote or in person), participants will complete screening measures through REDCap and an interview with study staff. Participants will also be shown a video to familiarize themselves with noxious thermal stimuli.

Eligible participants will be randomized to MB, SAV, or Sham MB, and starting in July, 2020, participants will only be randomized to SAV or Sham MB. The female to male ratio in RA is approximately 2-3:1^{71,72}, and RA is diagnosed at a higher rate in White Americans compared to African Americans.⁷³ To ensure these differences are accounted for, we will test sex and race as covariates in analyses.

Intervention Visits: Intervention sessions for each randomized condition will be one-on-one with an interventionist. Sessions (4 total) will take place via secure remote video conference (e.g., Zoom) or in the Johns Hopkins Behavioral Medicine Research Lab (BMRL) as dictated by COVID-19 conditions, and will last 20-minutes. Intervention visits will be scheduled 2 per week, so that the entire intervention will be completed in 2 weeks.

Intervention Descriptions

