Fatigue: PROMIS Fatigue is a 90 item bank that is available as a CAT or fixed length short forms.⁸⁹ It has been validated in an RA sample⁸⁶ and shown to have ecological validity.⁸⁷ We will use the short form included in the PROMIS-29A battery.

Disease Activity: The Clinical Disease Activity Index (CDAI)⁹⁰ is a composite clinical measure that includes a count of swollen joints (0-28), tender joints (0-28), a patient report of global disease activity (VAS 0-100) and a clinician report of global disease activity (VAS 0-100). This will only be administered under in-person conditions, and cannot be administered with participants who undergo remote baseline and intervention sessions.

Other Secondary Measures and Covariates

Mindfulness: The Five Facet Mindfulness Questionnaire (FFMQ)⁹¹ has 39 items on the mindfulness factors of observing, describing, acting with awareness, nonjudgment, and nonreactivity.

Savoring: The Savoring Beliefs Inventory (SBI)⁹² is a 14-item measure of one's perceptions about one's capacity to savor pleasant experiences in the past, present and future. It includes an 8-item subscale assessing perceived capacity to "savor the moment."

Positive and Negative Affect: The Positive and Negative Affect Schedule-X (PANAS-X)⁹³ is a 60-item measure assessing perceived intensity of various specific emotions, which are aggregated to form positive and negative affect scales, and series of subscales.

Depression and Anxiety: We will measure depressive and anxiety symptom severity using the PROMIS depression and anxiety items, respectively, and covary them in our analyses. We will use the short form included in the PROMIS-29A battery.

PROMIS-29A Battery: In addition to pain, pain interference, fatigue, depression and anxiety (described above), the PROMIS-29A Battery also assesses Ability to Participate in Social Roles and Activities, Physical Function, Sleep Disturbance, and Stiffness. We will administer the battery.

Self-Efficacy for Managing Symptoms: The PROMIS Self-Efficacy for Managing Symptoms (SEMS) CAT is based on a 28-item bank that includes assessment of the level of confidence to manage/control symptoms in different settings and to keep symptoms from interfering with work, sleep, relationships, or recreational activities. This has been recently validated in chronic conditions⁹⁴. We will use the short form, which is separate from the PROMIS-29A battery.

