Exclusion Criteria. 1) unstable medical or psychiatric morbidity within 3 months; 2) lifetime history of alcohol or substance use disorder; 3) current use of opioids (other than tramadol and/or codeine) for therapeutic or non-therapeutic purposes; 4) positive toxicology screen for recreational drugs; 5) pregnant or lactating women; 6) presence of any comorbid idiopathic (e.g., fibromyalgia) chronic pain condition; 7) prior meditation experience, with the exception of yoga; 8) cannot tolerate noxious thermal pain at any level above pain threshold; 9) contraindicated for MRI, assessed on an individual basis (e.g., metal devices, claustrophobia)

Plan for Medications. Current use of prescription opioids (other than tramadol and/or codeine) will be exclusionary because these medications directly influence corticostriatal circuits.¹⁰⁶⁻¹⁰⁸ Fewer than 2% of RA patients in the Johns Hopkins Arthritis Center—the primary recruitment site—are currently prescribed

opioids based on recent chart review. To ensure feasibility and promote generalizability, RA patients prescribed other medications commonly used in pain management, including antidepressants or non-opioid analgesics (e.g. NSAIDs), *will* be included. To minimize the impact of those allowable medications on primary aims, we will 1) ensure that patients are on a stable dose (>4 weeks) before enrolling in the study and that doses are anticipated to remain stable over the course of the study (confirmed by [name]); and 2) include medication classifiers as covariates.

6. Drugs/ Substances/ Devices

a. The rationale for choosing the drug and dose or for choosing the device to be used.

N/A

b. Justification and safety information if FDA approved drugs will be administered for non-FDA approved indications or if doses or routes of administration or participant populations are changed.

N/A

c. Justification and safety information if non-FDA approved drugs without an IND will be administered.

N/A

7. Study Statistics

a. Primary outcome variable.

Primary outcomes include brain function in the corticostriatal circuits.

b. Secondary outcome variables.

Secondary outcomes include experimental pain sensitivity, and RA clinical pain pain-related measures.

c. Statistical plan including sample size justification and interim data analysis.

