Data Analysis: fMRI data preprocessing will be performed using methods previously described in our work.^{18,19} Briefly, ASL images will be combined into a single CBF volume, and motion will be corrected using filters designed to minimize perfusion-based fluctuations. After these corrections are performed, global CBF will be calculated as a voxel-wise mean from the CBF volume. All non-fMRI variables will be checked for normality, and any non-normal outcome measures will be log-transformed as appropriate. Sex is an important biological variable in chronic pain¹⁰⁹, and we will report data disaggregated by sex.

However, due to the overrepresentation of females in RA, we are not powered to test for sex differences. In addition, a priori covariates will include sex, race, medication classifiers, age, clinical pain severity, depression symptoms, and anxiety symptoms, as each has been linked to variation in RA symptoms and other rheumatic diseases.^{26,110,111} Missing data will be handled by restricted maximum likelihood. If the missing-at-random assumption is violated, multiple imputation will be considered. Two-tailed p values ($\alpha = .05$) with 95% confidence intervals will be used to evaluate statistical significance.

The functional image analysis package FSL (FMRIB Software Library, Oxford, UK) will be used for first and second level statistical analyses. Functional images derived from CBF volumes are concatenated into a 4D volume for each individual, smoothed, normalized, and coregistered onto structural images using a standard nonlinear transformation.^{112,113} Next, regional signal changes in a priori regions (lOFC, putamen, vmPFC, and NAc) are assessed in first level, with T/F statistic images Gaussianized and cluster thresholded to correct for multiple comparisons across brain voxels.¹¹⁴

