Mixed effects modeling will be used as the primary analytic strategy for the primary outcomes. In our group therapy RCT design, mixed effects models permit the modeling of cohort-level random effects, as well as heterogeneous variance/covariance matrices to account for potential alpha inflation due to cohort-level clustering. We will test regional signal change in each ROI using mixed effects models examining within-person main effects of thermal stimulus (HEAT; i.e., painful vs. warm) and skill practice (PRACTICE; i.e., rest vs. active practice in the scanner during delivery of thermal stimuli), and the between-person main effect of intervention condition (CONDITION; i.e., MB vs. Sham MB vs. SAV), as well as their requisite 2-way and 3-way interactions. Thus, the HEAT X PRACTICE X CONDITION interaction will test the extent to which CBF in each a priori corticostriatal region varies during the active practice of either Sham MB, or SAV, relative to rest. Planned comparisons will test each of the HEAT X PRACTICE 2-way interactions within intervention groups to aid in the interpretation of the 3-way interaction.

Updated Statistical Approach due to Covid-19

Due to COVID-19 restrictions, we had to drop one arm from the study (Mindful Breathing). As such, a new statistical analysis plan was developed that we detail in the next section.

fMRI Pre-Processing: Imaging analysis was conducted using Functional Magnetic Resonance Imaging of the Brain (FMRIB) Software Library (Center for FMRIB, University of Oxford, Oxford, UK) and ASL data processing toolbox. Five subjects were excluded from analysis due to detected image artifact or excessive motion. A total of 29 subjects (15 SAV group, 14 NMB) were included in the final imaging analysis. Subjects underwent 8 functional (ASL) runs during the MRI challenge session. The 8 ASL images that resulted from the runs represented combinations of two experimental conditions: Pain (nonpainful warm stimulus vs. noxious heat) and Practice (no meditation vs. meditation). These combinations occurred in the following order: 1. warm + no meditation; 2. noxious + no meditation; 3. warm + no meditation; 4. noxious + no meditation; 5. warm + meditation; 6. noxious + meditation; 7. warm + meditation; 8. noxious + meditation.

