ASL images were motion corrected using the ASL MRI MoCo Method (Wang 2012). An additional motion correction and signal outlier filtering step was included (Tan et al 2009) to account for excessive motion and corruptive signal fluctuations. ASL images were converted into absolute CBF units according to the general kinetic model. The 8 CBF images were concatenated, intensity normalized, and then smoothed with a 9mm full-width half maximum (FWHM) Gaussian kernel. The images were spatially normalized to the MNI (Montreal Neurologic Institute) standard space using a 12-parameter affine transformation and then a nonlinear transformation. Additionally, a global white matter value was calculated for each CBF image by

extracting average white matter values from FSL's MNI152 white matter mask. The global white matter value was included in statistical models as a nuisance regressor.

Statistical Approach for fMRI: A group one-sample t-test ($n = 29$) was used to determine whole-brain, pain-related regions. The two Warm+No Meditation scans were subtracted from the two Noxious+No Meditation scans and then averaged. This average residual value per subject was used as the dependent measure included in the one-sample t-test.

Multiple regression analyses investigated the relationship between pain intensity/unpleasantness ratings and CBF during the Noxious condition. The 1st regressor consisted of the mean difference between the 2 Noxious+no Meditation scans vs Noxious+Meditation scans. The 2nd regressor included the percent change in subjects' pain intensity ratings from the Noxious+no Meditation to the Noxious+Meditation scans. The 3rd regressor included the percent change in the subjects' pain unpleasantness ratings from the Noxious+no Meditation to the Noxious+Meditation scans. All 3 regressors were orthogonalized to each other.

Because this was a proof-of-concept pilot mechanistic trial with a limited sample size, we set voxelwise threshold to 2.3, cluster corrected at $p=0.05$ (Worsley et al., 1992), in line with previous meditation-based imaging studies of similar size (Zeidan et al., 2015).

d. Early stopping rules.

We will report all adverse events and evaluate on a case-by-case basis whether the occurrence of a particular adverse event has implications for discontinuing the study to ensure participant safety and well-being.

8. Risks

a. Medical risks, listing all procedures, their major and minor risks and expected frequency.

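### The updated brain–pain regression lists no arm term and none of the seven a priori covariates, so an arm effect on both changes can pass for a brain–pain association

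*Combined protocol and SAP*

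**What the plan says.** Under Data Analysis (section 7c) the plan commits that "a priori covariates will include sex, race, medication classifiers, age, clinical pain severity, depression symptoms, and anxiety symptoms". Parts of this commitment appear elsewhere:

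- Section 4a, Screening and Randomization: "we will test sex and race as covariates in analyses".
- Section 4a, Other Secondary Measures and Covariates, on depression and anxiety symptoms: "and covary them in our analyses".
- Section 5, Plan for Medications: "include medication classifiers as covariates".

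The mixed model in section 7c also carried intervention condition as a between-person factor.

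After the mindful breathing arm was closed, the document says that "a new statistical analysis plan was developed that we detail in the next section". The detail that follows under Statistical Approach for fMRI has two parts. One is a one-sample test on 29 people of noxious against warm scans without meditation. The other is the regression: "Multiple regression analyses investigated the relationship between pain intensity/unpleasantness ratings and CBF during the Noxious condition". Its regressors are the difference between noxious scans with and without meditation, the percent change in pain intensity, and the percent change in unpleasantness. The text adds that "All 3 regressors were orthogonalized to each other". The only nuisance term named is global white-matter CBF. Arm and the seven covariates are not mentioned.

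**The concern.** Neither updated analysis, as written, compares savoring (SAV) with sham. The usual defence of an unadjusted analysis, that randomisation balances the groups, therefore does not apply. The regression asks whether people whose pain fell more also had a larger CBF change, and that is an observational question even inside a randomised trial.

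Arm is the obvious common cause. The trial's premise is that savoring raises corticostriatal activity relative to sham. If savoring also lowers pain ratings, the two arms form two clusters of points, and a line through both slopes even when neither cluster has a slope of its own. A reader could not then tell a brain mechanism of pain relief from a plain group difference. Orthogonalising the three regressors to one another does not help, because arm is not one of them.

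The silence on covariates adds a second problem. The stated reason for the new plan is the loss of one arm, which does not explain leaving out age, sex, medication, depression or anxiety.

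**Working it through.** **Inputs from the documents.** n = 29, split 15 (SAV) and 14 (labelled NMB in the update, taken here to be sham); three regressors plus white matter; seven a priori covariates; two-sided alpha 0.05. The plan gives no figure for this regression to reproduce. Its only power statement, 17 per group for over 80%, concerns the between-group contrast and has no bearing here.

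**Inputs assumed.** The size of the arm shift is not in the documents. A range of 0.5 to 1.0 within-arm SD is used, the same for pain change and CBF change. The check is one test on one region, not the cluster-corrected voxelwise map.

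**Step 1: covariate count.** Of the seven a priori covariates, none is listed in the updated regression. Arm is not listed either.

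**Step 2: expected spurious correlation from arm.** With unit variance and no association within arms, and a shift d in both variables, r = pq·d² / (1 + pq·d²), where pq = (15/29)(14/29) = 0.2497.

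- d = 0.5: 0.0624 / 1.0624 = 0.06
- d = 0.8: 0.1598 / 1.1598 = 0.14
- d = 1.0: 0.2497 / 1.2497 = 0.20

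**Step 3: false-positive rate of a single two-sided 5% test, by simulation at n = 29.**

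| Arm shift in both variables | Arm not in model | Arm in model |
|---|---|---|
| 0.5 SD | about 6% | about 5% |
| 0.8 SD | about 11% | about 5% |
| 1.0 SD | about 18% to 19% | about 5% |

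**Step 4: other omitted factors.** If a factor correlates a with rating change and b with CBF change, the spurious correlation is a × b. For assumed a of 0.1 to 0.5 and b of 0.3 to 0.5, this runs from 0.03 to 0.25, and the error rate from about 5% to 25%. The factor must act on the changes. In simulation, a stable factor that shifted only the levels of pain and CBF cancelled in simple differences (mean r 0.00, error 4.8%). One that added 0.6 SD per unit to both changes did not (mean r 0.26, error 29%).

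**Step 5: cost of adjustment.** This assumes one row per person, the first regressor carrying the mean, and one degree of freedom per added term.

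- As written, with white matter: 29 − 4 = 25 residual df, critical t 2.06.
- With arm: 24 df, critical t 2.06.
- With arm, medication classifier, age and sex: 21 df, critical t 2.08.
- With all seven covariates and no arm: 25 − 7 = 18 df. The smallest significant partial correlation rises from 0.38 to 0.44, and the value detectable with 80% power from 0.50 to 0.56.

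A separate intercept would make the first and third entries 24 and 20 df, with critical t of 2.06 and 2.09.

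**The case against.** **The covariates may not have been dropped.** The Data Analysis text still stands in the same document, and the figure of 29 is attached to the one-sample test, not to the regression. Both the removal of covariates and the pooling of arms are inferred from silence. This is right, so the point is that the regression as described lists neither. The document then supports two readings and must be reconciled.

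**Within-person changes already remove much confounding.** This also stands. Age, sex or long-term medication that only shift levels largely cancel. Two gaps remain: percent change may not fully remove baseline differences, and a factor acting on both changes does not cancel. Arm is such a factor under the trial's own hypothesis.

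**Adjusting for arm changes the question, and arm was never one of the seven covariates.** Arm was indeed a design factor in the mixed model, so its absence is a separate omission. But a brain–pain association offered as a mechanism should not arise only because two groups differ, so the arm-adjusted slope is the relevant one.

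**A stronger reading about opioids.** Section 5 says that "Current use of prescription opioids (other than tramadol and/or codeine) will be exclusionary because these medications directly influence corticostriatal circuits". A reader might infer that the medication classifier was the protection promised for tramadol and codeine users, and that it is now gone. The text does not say so. The exemption carries no named safeguard. The classifier is one of two measures for allowable medications, which most directly means antidepressants and non-opioid analgesics. The other measure, a stable dose, is untouched by the update. The same section puts opioid prescribing at the main recruitment clinic below 2%. If that count includes these two drugs, which is not stated, 29 × 0.02 gives under 0.6 expected users. A single user leaves the error rate at about 5%.

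**Conclusion.** The concern holds in limited form. As described, the updated regression has no arm term, lists none of the seven a priori covariates and gives no reason. Its slope is an across-person association that randomisation does not protect.

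The arm omission matters most. The roughly 11% to 19% false-positive rate rests on an assumed arm shift of 0.8 to 1.0 SD in both changes, no association within arms, and a single test at n = 29. If the shift is nearer 0.5 SD, the effect is negligible. The documents do not say which applies. The figures do not carry over directly to a cluster-corrected map.

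For the other covariates, confounding is possible but narrower, because only factors that alter both changes count. The documents support neither a claim that the covariates were knowingly discarded nor one that an opioid safeguard was withdrawn. The point is worth acting on because the remedy is cheap and the arm-adjusted slope is what a mechanistic reading needs.

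**What to change.** In section 7c, Statistical Approach for fMRI:

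1. Add arm (SAV against sham) to the regression and report the pain–CBF slopes adjusted for arm.
2. Add one sensitivity analysis with arm plus a short subset of the a priori covariates: the medication classifier as the protocol defines it, age and sex. No separate tramadol/codeine term is needed.
3. State that race, clinical pain severity, depression and anxiety are omitted because only 29 people are analysed, and reconcile this with Data Analysis and with the commitments in sections 4a and 5.
4. Because the update reports the analysis in the past tense, label these models as added after it.

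The cost is SAP wording and a rerun on variables the protocol already plans to collect. Arm takes one degree of freedom (25 to 24) and the sensitivity model about three more (to 21), so the critical t moves only from about 2.06 to 2.08. A medication classifier with several classes would cost somewhat more.

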Second, we propose that SAV will engage different aspects of the corticostriatal circuits. SAV is traditionally a non-mindful cognitive strategy that promotes positive emotions through focused attention on pleasurable thoughts or sensory experiences.⁶⁰⁻⁶² Importantly, positive emotions are linked to activity within two other critical corticostriatal structures: the ventromedial prefrontal cortex (vmPFC), which is associated with the regulation of positive emotions⁶³⁻⁶⁶, and the nucleus accumbens (NAc), which is associated with reward valuation in human and animal studies.⁶⁷⁻⁶⁹ Indeed Speer et al.⁷⁰ showed that NAc and vmPFC function were significantly augmented during a basic savoring task, and NAc function correlated with the experience of positive emotions.

We plan to use these data to inform a follow-up study in which we combine MB and SAV and determine whether the combination optimizes the engagement of corticostriatal circuits during noxious stimulation.

4. Study Procedures

- a. Study design, including the sequence and timing of study procedures (distinguish research procedures from those that are part of routine care).

Overview of Study

We aim to demonstrate that MB promotes lOFC and putamen activation and SAV promotes NAc and vmPFC activation during noxious thermal stimulation among RA patients. We will execute a randomized controlled trial (RCT) comparing two arms: SAV, and sham MB in 40 RA patients (n = 20 per group). Originally, we also randomized participants to a third arm (MB). However, due to the disruption of the COVID-19 pandemic, we will no longer randomize to MB, in order to optimize our ability to complete the project on budget. The screening and intervention sessions will take place either via secure remote video conference (e.g., Zoom), or at Johns Hopkins Bayview Medical Center, as dictated by fluid laboratory density needs and participant safety precautions. There will also be a post-intervention fMRI task, which will take place at University of Maryland-Baltimore (UMB). The fMRI visit is the only that will take place at UMB.

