Sample Size Estimation: The analysis plan outlined below includes simplistic models that ensure that we capture the main effects that we hypothesized. While more complex statistical models are plausible, the use of one- and two-sample t-tests allows us to confidently determine a sample size that achieves statistical

[figure not shown]

Figure 1. Left column: **The MB group significantly reduced pain ratings when compared to the sham-MB and control manipulations. *The sham-MB group significantly reduced pain ratings when compared to the control group. Right column: In the presence of noxious heat, mindfulness-based analgesia was associated with greater activation in the bilateral orbitofrontal cortex (OFC) and right putamen.

power based on previous work. Notably, this study is not powered for efficacy or effectiveness, but rather to observe intervention group differences on activation of corticostriatal circuits.

Zeidan and colleagues have repeatedly demonstrated^{18,19} that sample sizes ≥ 15 (per group) reliably detect the neural mechanisms supporting meditation-induced analgesia in both between and within-person designs. To more specifically power the study, we ran a preliminary analysis from a colleague's data set ([name]) and examined subjects' behavioral and neural (arterial spin labeling fMRI) pain responses before and after each group's respective interventions (MB vs. sham). As shown in Figure 1, while both sham MB and MB reduced pain, they did so via distinct brain mechanisms: MB-based analgesia was associated with greater activation in the bilateral OFC and right putamen¹⁸. We used a neuroimaging-based power calculation software (Neuropowertools) and entered the contrast of parameter estimates from the preliminary analysis in Figure 1. Our simulation indicated that $n=17/\text{group}$ will provide over 80% power to test the hypotheses that interventions have differential effects on corticostriatal activation during noxious thermal stimulation, correcting for multiple comparisons. To account for loss of degrees of freedom due to random cluster effects associated with the randomization, we will target $n=20/\text{group}$ ($N=40$ total) for the R61 phase.

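### As described, the brain-pain regression fits one slope per pain rating with no arm term, so it cannot show whether an association belongs to savoring or to Sham

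*Combined protocol and SAP*

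**What the plan says.** The updated approach in section 7c gives the analysed sample: "A total of 29 subjects (15 SAV group, 14 NMB) were included in the final imaging analysis". NMB is not defined there; I take it to be the Sham MB control arm.

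Two analyses follow under Statistical Approach for fMRI. The first is a one-sample test on all 29 people, using only the scans without meditation. The second is the brain-pain regression: "Multiple regression analyses investigated the relationship between pain intensity/unpleasantness ratings and CBF during the Noxious condition". Three regressors enter it:

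- a practice contrast under noxious heat, comparing the runs without and with meditation;
- change in pain intensity, given as a single column: "The 2nd regressor included the percent change in subjects' pain intensity ratings from the Noxious+no Meditation to the Noxious+Meditation scans";
- the matching single column for unpleasantness.

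The list closes with "All 3 regressors were orthogonalized to each other". A white-matter nuisance value is also used. No arm indicator, arm-by-rating term or separate fit by arm is described.

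The mixed model set out before the COVID-19 update contains intervention condition and its interactions, with planned comparisons inside each group. It models CBF and has no pain-rating slope. The section then says that a new analysis plan was developed.

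**The concern.** Of the two analyses in the updated approach, the regression is the only one that uses the meditation scans and the only one that relates change in pain to CBF. The abstract gives the neural mechanism of pain relief as the study's purpose, and the remaining comparison is SAV against Sham.

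With one column per rating, all 29 people share one slope for intensity and one for unpleasantness. A significant region could then reflect an association in SAV, in Sham or in both, and the model cannot tell these apart. An association confined to SAV would be diluted by the 14 Sham patients.

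A Sham association cannot be dismissed. Section 4a says the sham training is not a neutral control, section 7c reports that sham reduced pain in the preliminary data, and section 9a counts sham as an active breathing intervention.

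An arm intercept or a comparison of mean CBF between arms would be useful, but either would still leave one shared slope.

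**Working it through.** **Inputs from the plan.** n = 15 SAV and 14 control; one column per rating; two-sided 0.05 (section 7c, Data Analysis).

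**Assumed inputs.** The documents give no within-arm correlation between pain change and CBF change. I use 0.3 to 0.7, with 0 and negative values for contrast.

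**The plan's own figure.** Section 7c states over 80% power at 17 per group. That figure concerns group differences in activation, not a brain-pain slope, and the parameter estimates given to the power software are not reported. It cannot be reproduced, and nothing below depends on it.

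**Step 1: what the common slope estimates.** With equal arm means and equal spread of pain change in both arms,

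pooled slope ≈ (15/29) × SAV slope + (14/29) × Sham slope = 0.517 × SAV + 0.483 × Sham.

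- SAV 0.6, Sham 0: 0.517 × 0.6 = 0.31, about half the SAV slope.
- SAV 0, Sham 0.6: 0.483 × 0.6 = 0.29, although SAV has no association.
- SAV +0.6, Sham −0.6: (0.517 − 0.483) × 0.6 = 0.02, almost complete cancellation.

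**Step 2: signal for a SAV slope.** In units of slope/residual SD, the noncentrality is √15 = 3.87 within SAV and (15/29) × √29 = 2.79 pooled when Sham is zero, a loss of 28%. If the Sham slope is k times the SAV slope, the two are equal when 0.517 + 0.483k = √(15/29) = 0.719. This gives k = (0.719 − 0.517)/0.483 = 0.42. Above roughly that ratio, pooling has the stronger signal.

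**Step 3: simulation.** Bivariate normal pain change and CBF change within arm, 15 + 14 people, equal arm means, one rating, one location, no cluster correction, 20,000 to 40,000 data sets per case. The table gives the percentage significant at two-sided 0.05.

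| SAV r | Sham r | Pooled slope | SAV slope, SAV only |
|---|---|---|---|
| 0 | 0 | 5 | 5 |
| 0 | 0.3 | 12 | 5 |
| 0 | 0.5 | 26 | 5 |
| 0 | 0.6 | 35 | 5 |
| 0 | 0.7 | 45 | 5 |
| 0.6 | 0 | 40 | 70 |
| 0.7 | 0 | 50 | 88 |
| 0.6 | −0.6 | 9 | 70 |
| 0.6 | 0.3 | 72 | 70 |
| 0.6 | 0.4 | 82 | 70 |
| 0.6 | 0.6 | 95 | 70 |

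Adding an arm intercept changes the pooled figures by at most about 2 points when arm means are equal.

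**Step 4: sensitivity to the set-up.** With two independent ratings and unit residual SD in each arm, the Sham-only pooled figures at 0.5/0.6/0.7 are 27/39/55%. At SAV-only 0.6 the figures are 44% pooled and 66% within SAV. The direction is the same and the sizes are similar.

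**Step 5: arm means.** In that second set-up, with no association inside either arm but arm means 1 SD apart on both rating and CBF, the model without an arm term is significant in 18% of data sets. With an arm term it is 5%.

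**Step 6: the slope difference.** Power is about 36% at 0.6 against 0, and 13% at 0.6 against 0.3.

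**The case against.** **Pooling is inferred.** The figure of 29 is attached to the one-sample test; the regression sentence gives no n and speaks of analyses in the plural. Separate fits by arm are not excluded. This stands as a caveat. The closed list of regressors makes pooling the likelier reading, and if fits were made by arm, the text should say so.

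**The plan does not predict different slopes for SAV and Sham.** A reader might infer that its premise is pain relief through different circuits in these two arms. The documents do not support that. The statement that "while both sham MB and MB reduced pain, they did so via distinct brain mechanisms" concerns MB, the dropped arm, in a colleague's data set. The sentence "Second, we propose that SAV will engage different aspects of the corticostriatal circuits" contrasts SAV with MB. The objectives and primary outcome concern activation by intervention, and arms can differ in mean activation while sharing one brain-pain slope. This objection stands. The point that remains is narrower: the model cannot show whether the slopes differ.

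**Pooling can be the better test.** A reader of the zero-slope and opposite-slope cases alone might infer that pooling helps only if the slopes are identical. The 0.6/0.3 and 0.6/0.4 rows show otherwise, and because sham also reduced pain, partly shared slopes are plausible. This is why the pooled slope should be kept.

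**The remedy has low power and comes late.** Both are true, and both are reflected in how the added analysis should be labelled and reported.

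**Conclusion.** The point holds in a limited form. On its natural reading, the regression estimates an average association over both arms, and a significant result cannot be credited to savoring.

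Under the assumed correlations, a Sham-only association of 0.3 to 0.7 produces a significant pooled slope in about 12% to 45% of data sets. It would be wrong to read this as an inflated type I error: when Sham has a slope the pooled null is false, and when neither arm has one the rate is 5%. The error lies in attribution, and arises only if the result is presented as a savoring mechanism. The plan does not say that it will be.

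For a SAV-only association of 0.6, detection falls from about 70% to about 40%. That loss disappears once the Sham slope is about half the SAV slope or more.

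These sizes rest on assumed correlations at a single location, one rating, equal arm means, no white-matter regressor and no cluster correction. They show the scale of the problem and do not predict the trial's results.

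**What to change.** In section 7c, Statistical Approach for fMRI:

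1. State whether the regression pools the arms, and its n.
2. Keep the pooled slope, fit it with an arm term, and label it as an average over both arms.
3. Add a model with arm-specific rating slopes: each rating centred within arm, with separate arm means. Report the SAV slope, the Sham slope and their difference with 95% CIs.
4. Base statements about savoring on the SAV slope. Base statements that an association is specific to savoring only on the difference, never on one slope being significant and the other not.
5. Label the addition a post-results amendment, because this part of the plan is written in the past tense.

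The cost is a change of wording and one further run of the group-level design on existing data. Splitting three columns into six leaves 29 − 6 = 23 residual degrees of freedom instead of 26, before any nuisance term. The SAV slope will be less precise than the pooled slope if the arms share one slope. Given its low power, the slope difference should be presented as an estimate with its interval; a non-significant difference would not show that the slopes are equal.
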